Menschen verbringen die meiste Zeit in Innenräumen unter suboptimalen Lichtverhältnissen, was zunehmend als Risikofaktor für die steigende Häufigkeit von Herz-Kreislauf-, Stoffwechsel- und psychischen Erkrankungen in der alternden Gesellschaft angesehen wird. Lichtexposition kann den Blutzucker, den Blutdruck und das psychische Wohlbefinden beeinflussen. Daher können schlechte Lichtverhältnisse im Alltag zu der zunehmenden Belastung des Gesundheitssystems im Zusammenhang mit einer alternden Bevölkerung beitragen. Außerdem ist bekannt, dass die Lichtempfindlichkeit im Alter abnimmt (z. B. aufgrund der altersbedingten Degeneration der Augenstrukturen), was positive gesundheitliche Auswirkungen von Licht abschwächen kann. Derzeit ist jedoch weitgehend unbekannt, wie sich die Lichtexpositionsgewohnheiten und die Sensitivität gegenüber den gesundheitlichen Auswirkungen von Licht mit dem Alter verändern. Ebenso ist unklar, inwieweit Unterschiede in der Lichtempfindlichkeit von der Degeneration der Linse und der Netzhaut abhängen. In dieser Studie sollen alltägliche Lichtverhältnisse jüngerer und älterer Erwachsener charakterisiert und im Zusammenhang mit kardiovaskulärer, metabolischer und psychischer Gesundheit betrachtet werden. Konkret wird ein ambulanter Erhebungsansatz über 12 Tage angewendet, bei dem physiologische Parameter und alltägliche Gedanken, Verhaltensweisen und Erfahrungen verschiedener Altersgruppen mit Hilfe von tragbaren Technologien (z. B. Lichtsensoren, Aktivitäts-Tracker, kontinuierliche Blutzuckermessgeräte) und Smartphone-basierten Selbstberichten (z. B. Stimmung, Vitalität) gemessen werden. Zu Beginn der Studie wird die Degeneration der Linse und der Netzhaut der Teilnehmenden durch Augenärzte objektiv quantifiziert. An den letzten zwei Tagen werden die Teilnehmenden in randomisierter Reihenfolge einen Arbeitstag bei schwachem und einen weiteren bei hellem Licht unter demselben Messprotokoll wie zuvor verbringen, sodass jede Person sowohl einen Bürotag bei schwachem Licht und einen Tag bei hellem Licht verbringt (randomisiertes Cross-over Design). Auf diese Weise wird die individuelle Lichtempfindlichkeit und deren gesundheitliche Auswirkungen experimentell bewertet. Die Teilnehmenden erhalten als Aufwandsentschädigung nach Beendigung der Studie 200 € und bekommen zudem Rückmeldung über ihre alltäglichen Blutzucker- und Blutdruckwerte, sowie eine detaillierte Augenuntersuchung. Dieses Projekt wird dazu beitragen, den Einfluss von Licht auf Gesundheitsparameter im Alltag besser zu verstehen und langfristig gesunde Beleuchtungskonzepte in verschiedenen Gebäudetypen für unterschiedliche Altersgruppen zu ermitteln.

1. Background

Within a day, the Earth rotates once around its own axis, causing predictable changes in light conditions throughout the day. In this context, humans have developed the ability to synchronize their physiological processes to a period length of around 24 hours, adapting to these recurring fluctuations. Our ambient light hence has a major influence on our physiology and psychology depending on the time of day. However, over the last century our relationship to light has drastically changed: our current “indoor society” spends about 90% of awake time indoors exposed to lower light intensities (e.g. up to 300 lux for typical electric office lighting) than outside in natural daylight (e.g. up to 100,000 lux on a sunny day), along with excessive exposure to artificial light during the evening beyond sunset. Yet, studies on the impact of daytime light exposure patterns are limited (Fleury et al., 2020). A chronic lack of daylight in combination with excessive light in the evening is increasingly being considered as a risk factor in the aging society's rising incidence of cardiovascular, metabolic, and psychological disorders. For example, experiencing darker days and brighter nights was associated with a higher risk for the onset of several psychological disorders such as depression or psychosis (Burns et al., 2023). In terms of short-term effects on potential mediating mechanisms, Harmsen et al. previously showed that bright light during office hours induced mostly favorable acute effects on glucose control and thermoregulation in older insulin-resistant volunteers compared to dim light (Harmsen et al., 2022) and that natural office lighting through windows improved glucose control in older type 2 diabetes patients (Harmsen et al., 2022). Similarly, when workers were exposed to higher levels of light during their workday, they reported increased vitality and lower depressive symptoms (Mariana G. Figueiro et al., 2017; Nagare et al., 2021). However, to date, there is only limited data on how light exposure patterns differ across the lifespan (Scheuermaier et al., 2010) and how aging may affect the influence of light on our physiology and psychology. First findings indicate that younger and older adults show different emotional effects of exposure to blue light (Sletten et al., 2009), but these differences have so far not been addressed in daily life.

Growing evidence suggest that the effects of light on health parameters vary dramatically across individuals, yet recommendations for appropriate light exposure in real-life settings rarely take these individual differences into account (Chellappa, 2021). In this context, age has been identified as a moderator of light sensitivity (Chellappa, 2021), but the underlying mechanisms remain elusive. Therefore, this interdisciplinary project will for the first time explore the contribution of aging processes within the eye to an individual's sensitivity to light and its health effects. The degeneration of the lens associated with cataract is a natural aging process that affects the amount of light that can reach the retina. Cataract affects around 17% in the general population worldwide and up to 54% in the over-60 age group (Hashemi et al., 2020). Replacing the lenses of the eye by surgery largely restores light transmission and has been shown to improve the sleep-wake rhythm, the release of the sleep hormone melatonin, light sensitivity, and sleep quality (Brøndsted et al., 2017; Giménez et al., 2016). Depending on how far the degeneration of the lens and retina have progressed and/or whether surgical intervention has taken place, large individual differences in sensitivity to different ambient light can therefore be expected. However, this aging process is ignored by most previous attempts to study the physiological and psychological health effects of light.

2. Aim of the study

With the primary hypothesis of this study being that younger and older individuals differ in their light exposure patterns in everyday life, the two main goals of the AgeLight study are to:

- characterize light exposure patterns in younger and older adults and their link to cardiovascular, metabolic, and psychological health
- identify determining factors of an individual's sensitivity to light and its health effects (such as degeneration of the lens and retina)

3. Study design

This study is designed as an observatory field study of characterizing younger and older adults' everyday life in terms of light exposure patterns as well as cardiovascular, metabolic and psychological health parameters over 10 days continuously through wearables and smartphone-based self-reports (ambulatory assessment period). On the first day of data collection, each participant will undergo an eye examination at the Institute of Ophthalmology. Thereafter participants start wearing the wearable sensors and instructions on how to complete the smartphone-based self-report forms are provided. Data will be collected from the first evening onwards (ca. 18:00 h). After the ambulatory assessment period under free-living conditions, participants will spend the 11th and 12th day in a controlled office room environment from 08:30 to 17:00 h. In a randomized cross-over design, the 11th and 12th day will be spent in either bright (1250 lux) or dim office lighting (10 lux). On these days, participants will continue to wear the wearables and complete the same smartphone-based self-reports as over the 10-day ambulatory assessment period. Between day 11 and 12, participants will leave controlled conditions from 17:00 h on day 11 to 08:30 h on day 12. On day 11 and 12, participants will receive a standardized fluid meal for breakfast and a bread-based meal for lunch, and are otherwise instructed to avoid any food, caloric or caffeinated beverages between 08:30 and 17:00 h. After removing all wearables on day 12, the study ends at 17:30 h. Over these 12 days of data collection, participants will be asked to keep their bedtimes at home as consistent as possible between days, and on day 11 and 12 they will be instructed to come to the office facilities fasted without any caloric intake after 22:00 h on the previous evening of day 10 and 11, respectively.

To minimize the burden on participants in this study, we use mobile and user-friendly devices for data collection and give clear instructions for data collection. We keep individual assessments short, limit the study duration to 12 days and provide incentives for participation (up to €200 reimbursement). On day 11 and 12, participants are mostly free to do whatever they like to do while being in the office environment (e.g. watching movies, paperwork, reading, video-meetings etc.).

[figure not shown]

Fig.1. Overview of study design.

4. Responsibilities

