4.4. Registration

The study will be registered on osf.io.

5. Participants

30 healthy younger adults and 30 healthy older adults.

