8.3 Descriptive statistics

Statistical analysis will be performed using the statistical computer programs SPSS for Mac OS (version 25, IBM) and R Studio for Windows. Descriptive statistics will be reported for all data parameters and will be reported as minimum, maximum, mean, standard deviation (SD) and intraindividual standard deviation (iSD) for data assessed in daily life, and/or standard error of the mean (SEM). As a measure of dispersion, SD will be used for descriptive statistics of the assessed data, while the SEM will additionally be reported for the results of the primary and secondary outcomes.

In case of non-normality, values will either be transformed using log transformation or non-parametric tests will be used. In addition, Pearson correlation coefficients will be computed to correlate parameter values. The unpaired Students t-test will be used to compare outcome measures between the young and old group. Due to the randomized cross-over design, to compare outcomes between the bright and dim office light condition irrespective of age (secondary outcome), a paired t-test will be conducted. Differences will be considered statistically significant when tested two-sided $p < 0.05$. Missing values will not be replaced. We will apply a full information approach using all available data from all participants.

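### Caffeine is restricted on the office days only from 08:30, while the overnight rule covers calories alone, so caffeine before arrival may differ between the bright and dim days

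*Protocol*

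**What the plan says.** Protocol section 3 (Study design) sets two intake rules for days 11 and 12.

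- During the session, apart from the standardised breakfast and lunch, participants are "otherwise instructed to avoid any food, caloric or caffeinated beverages between 08:30 and 17:00 h".
- Before the session, they must "come to the office facilities fasted without any caloric intake after 22:00 h on the previous evening of day 10 and 11, respectively".

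The only mention of caffeine is in the first rule. Section 6.5 repeats the schedule and adds nothing on caffeine. Between the two sessions, "participants will leave controlled conditions from 17:00 h on day 11 to 08:30 h on day 12".

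The order of bright (1250 lux) and dim (10 lux) light is randomised, with one day per condition. Section 8.3 states the analysis: "to compare outcomes between the bright and dim office light condition irrespective of age (secondary outcome), a paired t-test will be conducted". It names no caffeine term. The planned sample is "30 healthy younger adults and 30 healthy older adults" (section 5), so up to 60 pairs.

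Section 6.3.4 asks participants to photograph everything they eat or drink other than water. It does not say that the photographs will be used to check intake before the office sessions.

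**The concern.** By barring caffeine during the session, the protocol treats it as something to hold constant. It also standardises meals, fasting and bedtimes so that the two days are comparable. The caffeine restriction nevertheless starts only at arrival. Read literally, a black coffee at 08:15 breaks no rule and one at 08:35 does.

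With one day per condition, a coffee on one morning only goes straight into that person's bright-dim difference. Two uses of the data are exposed:

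- the paired test on the office-day outcomes. Blood pressure and skin temperature are recorded only on these two days (section 6.4), so there are no free-living readings to fall back on;
- the individual differences. Section 2 makes the determinants of individual light sensitivity a main goal, and the German summary says the two office days assess that sensitivity experimentally. Randomised order protects the group mean in expectation. It does not protect one person's difference from an unequal morning.

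**Working it through.** **1. The two windows side by side**

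| Interval on each office day | Calories | Caffeine |
|---|---|---|
| 22:00 to 08:30 (2 + 8.5 = 10.5 h) | barred | not mentioned |
| 08:30 to 17:00 (8.5 h) | barred apart from study meals | barred |

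The pre-arrival fast is spelled out by calories alone, so a calorie-free caffeinated drink breaks neither rule. The uncontrolled interval between the sessions, 17:00 to 08:30, lasts 7 + 8.5 = 15.5 h.

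**2. Noise (illustration)**

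The plan has no figure to reproduce here. Everything about caffeine below is assumed. Let c be the caffeine effect in SDs of the paired difference, and p the probability of a pre-arrival coffee, independent on each morning.

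- Share of participants with coffee on one morning only: 2p(1−p), which is 37.5% at p = 0.25 and 50% at p = 0.5.
- Variance factor of the paired difference: 1 + 2p(1−p)c².
- Reference effect with 80% power at n = 60, two-sided 0.05, normal approximation: (1.960 + 0.842)/√60 = 0.362 SD.
- Power with the extra noise: Φ(2.802/√factor − 1.960).

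| c | Variance factor (p = 0.25; 0.5) | Power (p = 0.25; 0.5) |
|---|---|---|
| 0.25 | 1.023; 1.031 | 79.1%; 78.8% |
| 0.5 | 1.094; 1.125 | 76.4%; 75.2% |
| 1.0 | 1.375; 1.500 | 66.6%; 62.8% |

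For c = 0.5 and p = 0.5: 1 + 0.5 × 0.25 = 1.125, and Φ(2.802/1.061 − 1.960) = Φ(0.681) = 75.2%.

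Independence is unfavourable. With stable habits fewer people differ between mornings, and the added variance shrinks towards zero.

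**3. Could it bias the contrast?**

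Assume equal numbers in each order, and that the order is not disclosed before day 11 (the protocol does not say). Only the day-12 morning can then react to a known condition. Let r be the share taking caffeine on day 11, and d and b the shares on day 12 among those expecting dim and bright.

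- Dim mornings: (r + d)/2. Bright mornings: (r + b)/2.
- Overall imbalance: (d − b)/2, half of any day-12 difference.

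An overall imbalance of 10 points therefore needs a 20-point difference on day 12. It would give a bias of 0.10 × c, which is 0.025, 0.05 or 0.10 SD for c = 0.25, 0.5 or 1.0. The two-sided type I error, Φ(bias × √60 − 1.960) + Φ(−bias × √60 − 1.960), would then be 5.4%, 6.7% or 12.1% instead of 5%. If d = b, the bias is zero.

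**The case against.** The two sentences do not contradict each other: one sets a metabolic fast before the standardised breakfast, the other sets conduct in the office. Participant instructions are not among the documents and may define the fast as water only. Drink photographs already record intake and could support a sensitivity analysis. Stable habits largely cancel within a person. The affected comparison is secondary.

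Most of this stands, and it limits the weight of the point. It does not close the gap. The protocol text fixes the start of the caffeine restriction at 08:30, photographs neither prevent nor equalise intake, and an analysis plan cannot standardise the mornings afterwards.

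A reader might go further and infer that the bright-dim contrast is biased, because 1250 against 10 lux is obvious and participants know the day-12 condition once day 11 is over. The documents do not support that. The order is randomised, and on the assumptions above any reaction is confined to day 12 and halved overall. Its direction is also open: someone expecting a dim day and someone coming off one are about to enter opposite conditions, so the two reactions can offset each other. A rise in day-12 coffee common to both orders is a period effect, which the randomised order balances in expectation. Nor do the documents give any figure for how much, or for how long, caffeine shifts the outcomes.

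**Conclusion.** The point holds as a minor design weakness. As written, the rules permit calorie-free caffeine during the 10.5 h before each office session and do not require it to be equal on the two days. The result is avoidable noise in the secondary paired comparison and in individual light-sensitivity differences. On the assumed inputs the loss of power ranges from about 1 percentage point (c = 0.25) to about 13 to 17 points (c = 1.0), and is about 4 to 5 points at c = 0.5. A bias is possible only if intake depends on the condition; its size and sign cannot be derived from the documents. The primary analyses in section 8.4 compare everyday light exposure between age groups and are not affected. This judgement rests on the protocol text alone; a further rule in the participant instructions would reduce or remove the concern.

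**What to change.** In section 3, make pre-arrival caffeine equal on both office mornings, in one of two ways:

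- start the caffeine restriction at 22:00 on the evenings of days 10 and 11, together with the existing caloric restriction, and keep it to 17:00; or
- require the same pre-arrival intake on day 12 as on day 11.

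In either case, record intake at arrival with one yes/no question on each day, and check the answer against the m-Path drink photographs.

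The cost is a few words in the protocol and the participant instructions, plus one question per office day. Aligning the windows lengthens the restriction from 8.5 h to 10.5 + 8.5 = 19 h, mostly overnight. That may affect sleepiness ratings in habitual drinkers, though equally under both conditions. Requiring the same intake avoids the longer abstention but relies on participants repeating their day-11 morning.

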4.3. Financing

The project is funded by the Federal Ministry of Education and Research (BMBF) and the Ministry of Culture and Science of the State of North Rhine-Westphalia (MKW) as part of the Excellence Strategy of the Federal and State Governments, supplemented by funds from the LuF Healthy Living Space (basic funding of the endowed professorship funded by VILLUM FONDEN, [name], (<https://veluxfoundations.dk/en>) a Danish foundation.

4.4. Registration

The study will be registered on osf.io.

5. Participants

30 healthy younger adults and 30 healthy older adults.

5.1. Inclusion Criteria

- Age: 18-35 or 60-80 years old
- Voluntary participation, signed consent form
- Owns an Android or iOS Smartphone compatible with the m-Path App
- Generally healthy (self-reported)
- Non-smoker for at least 12 months (self-reported)

5.2. Exclusion criteria

- Pregnancy (for female participants) (self-reported)
- Night-shift worker
- Eye diseases (e.g. glaucoma, age related macular degeneration, diabetic retinopathy conditions after retinal detachment / retinal blood vessel occlusions)
- Pseudophakic eyes
- Psychological disorders: insomnia, depression, bipolar disorder and generalized anxiety disorder
- Wearing specially-filtered glasses

5.3. Scheduling

The 12 days of testing will take place after an initial phone call screening. Participants can leave the study at any time for any reason if they wish, without any consequences. The investigator may decide to remove a participant from the study for urgent medical reasons. Participants may be removed from the study if they do not adhere to the study procedure. After elimination, there is no follow-up examination of the participant. In case of withdrawal due to medical complications, the participant is referred to a general practitioner.

5.4. Recruitment

Participants are recruited via advertisements on billboards at the RWTH Aachen University Hospital and in newspapers as well as websites.

6. Methods

6.1. Study Timeline

The study will be conducted between November 2024 and May 2025.

6.2. Participants and Groups

The two comparative groups formed in this study consist of 30 younger adults (18-35 years) and 30 older adults (60-80 years), both females and males will be included, and the aim is to match both groups with respect to sex (i.e. ideally 15 women and 15 men per group). The age contrast in the two groups is chosen, as substantial differences in degeneration of the lenses and retina within the eye can be expected.

For the sample size calculation of $n = 30$ per group, we refer to Zauner et al. (Zauner et al., 2023), who created a procedure to calculate statistical power and required sample size for wearable light-logging data. For most light-logging metrics, their approach shows that for strong differences in light exposure patterns (i.e., winter vs. summer) even smaller samples are sufficient ($n = 3-24$). We do not expect that differences between age groups are that strong as seasonal differences. However, we are confident that effects of about $d = 0.7$ could be detected with our design ($n = 30$ per group).

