8.4 Primary and secondary study parameters

As the primary hypothesis of this study is that younger and older individuals differ in their light exposure patterns in everyday life, the primary outcome of this study is melanopic equivalent daylight illuminance (M-EDI) quantified in lux by the Actlumus wearable light sensor. M-EDI may differ between groups with respect to overall daily levels, exposure levels at different times of day (work-day vs. weekend-day), and the difference in exposure levels between work-days and weekend-days. Therefore, M-EDI will be statistically analysed between groups in the following three ways:

1. Compare the area under the curve (AUC) of M-EDI from day 1 to day 8 between young and old (unpaired t-test)

2. Averaging exposure levels over work-days and weekend-days in 1-hour time intervals over 24 hours and compare the two average 24-hour M-EDI patterns between young and old (2-way repeated measures ANOVA, factor 1 (between-subjects) group, factor 2 (within-subjects) time)
3. Averaging the onset of M-EDI in the morning hours and the offset in the evening over work-days and weekend-days and calculate the difference in onset and offset between the averaged work-day and weekend-day between groups (unpaired t-test)

The secondary hypotheses are that light exposure patterns in everyday life are linked to daily metabolic, cardiovascular and psychological outcomes, and that this link is stronger in individuals displaying less degeneration of eye structures.

Accordingly, mixed effects regression analyses will be performed to assess the relationship between different aspects of daily light exposure (momentary M-EDI, average daily exposure level, onset/offset; independent variables) and each of the daily health parameters (metabolic, cardiovascular, psychological functioning, and sleep; dependent variables). To evaluate the role of the degree of eye degeneration, an interaction term between light exposure and eye degeneration will be added to the regression models.

9 Ethics

The study must be approved by the Ethics Committee of RWTH Aachen University. The study is carried out in accordance with the Declaration of Helsinki (the latest version, established in Fortaleza, Brazil, 2013) and the Law on Medical Research involving Human Beings (WMO) and the General Data Protection Regulation (GDPR or GDPR).

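### The age groups are to be balanced on sex only as an aim, yet no primary analysis contains sex; adding it (and day length) is a cheap, minor improvement

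*Protocol*

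**What the plan says.** - **Design (Protocol 6.2).** For two groups of 30, "the aim is to match both groups with respect to sex (i.e. ideally 15 women and 15 men per group". Sex is the only factor named for balancing. No quota is set, and nothing says what happens if the target is missed. Recruitment is by open advertisement (5.4, 9.3).
- **General rule (Protocol 8.3).** "The unpaired Students t-test will be used to compare outcome measures between the young and old group". Tests are two-sided at 0.05. Log transformation or non-parametric tests are allowed under non-normality.
- **Primary analyses (Protocol 8.4).** First: "Compare the area under the curve (AUC) of M-EDI from day 1 to day 8 between young and old (unpaired t-test". Second: a repeated measures ANOVA with "factor 1 (between-subjects) group, factor 2 (within-subjects) time". Third: "calculate the difference in onset and offset between the averaged work-day and weekend-day between groups (unpaired t-test". None includes sex or any other covariate.
- **Sample size (Protocol 6.2).** The authors are confident that "effects of about $d = 0.7$ could be detected with our design ($n = 30$ per group". No power is stated. The same paragraph treats winter versus summer as a strong difference in light exposure.
- **Data available.** Phone screening (6.3.1) records gender with four options: female, male, diverse, or no answer. The study runs from November 2024 to May 2025 (6.1).

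**The concern.** The protocol considers sex important enough to balance between the age groups, then leaves it out of every primary comparison. Age group is not randomised, so apart from recruitment toward the target nothing protects the contrast from an uneven sex mix. Two things can follow, depending on how recruitment goes:

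- If the groups end at 15/15, any variance in light exposure due to sex stays in the error term and the test is slightly conservative.
- If they do not, part of a sex difference is read as an age difference.

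The protocol itself names the primary tests, so this is a choice already fixed rather than a detail left to a later analysis plan. Season raises a parallel question. The study spans months of very different daylight, and the protocol states no balancing of the age groups over them.

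**Working it through.** **Inputs from the protocol.** n = 30 per group and d = 0.7 (6.2); two-sided 0.05 (8.3); target split 15/15 (6.2).

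**Assumed input.** The protocol gives no sex effect on melanopic EDI. Let *s* be the difference between women and men in within-group SD units, shown for 0.2, 0.3 and 0.5. With an even split, sex explains *s*²/4 of the within-group variance.

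**Step 1: the plan's own figure.** The standard error of the difference is √(1/30 + 1/30) = 0.258 SD, so the noncentrality is 0.7/0.258 = 2.71. With 58 degrees of freedom the power is 76.0%. Since no power is stated, the claim that d of about 0.7 could be detected can be neither confirmed nor refuted.

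**Step 2: balance reached (15/15).** With sex in the model the residual SD is √(1 − *s*²/4), the noncentrality is 2.71 divided by that, and 57 degrees of freedom remain.

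| *s* | share of variance | SE ratio, adjusted to unadjusted | power without sex | power with sex |
|---|---|---|---|---|
| 0 | 0 | 1.000 | 76.0% | 76.0% |
| 0.2 | 1.0% | 0.995 | 76.0% | 76.4% |
| 0.3 | 2.25% | 0.989 | 76.0% | 76.9% |
| 0.5 | 6.25% | 0.968 | 76.0% | 78.6% |

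The gain is 0.4 to 2.6 percentage points for *s* from 0.2 to 0.5. By simulation (100,000 runs), the unadjusted test has a type I error of 4.8% at *s* = 0.3 and 4.2% at *s* = 0.5, so it errs on the safe side.

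**Step 3: balance missed (18 versus 12 women, chosen for illustration).** Bias of the unadjusted contrast = (18/30 − 12/30) × *s* = 0.2*s*.

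| *s* | bias in SD | as share of d = 0.7 | in standard errors (÷ 0.258) |
|---|---|---|---|
| 0.2 | 0.04 | 5.7% | 0.15 |
| 0.3 | 0.06 | 8.6% | 0.23 |
| 0.5 | 0.10 | 14.3% | 0.39 |

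The simulated type I error is 5.3% at *s* = 0.3 and 6.0% at *s* = 0.5. The direction of the bias depends on the sign of the sex effect, which is unknown.

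**Step 4: price of adjustment under that imbalance.** The correlation between group and sex is 0.6 − 0.4 = 0.2. The variance inflation is 1/(1 − 0.04) = 1.042, so the SE is √1.042 = 1.021 times as large if sex has no effect. The adjusted SE becomes the smaller one only if sex explains more than 4% of the variance, that is *s* above about 0.4. At *s* = 0.3 the ratio is √(0.9775/0.96) = 1.009, about 1% wider; at *s* = 0.5 it is √(0.9375/0.96) = 0.988, about 1% narrower.

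**The case against.** The strongest reply is that nothing here is an error. The matching is at group level, not in pairs, so an unpaired test suits the design, and at 15/15 its type I error stays at or below 5%. Harm requires a sex effect that the protocol does not report; with none, power is 76.0% either way. Sex is known at screening, so a large imbalance can be avoided during enrolment. All of this stands, and it is why the point is minor. It does not remove the point: the balance is only an aim, no quota enforces it, and the choice to balance on sex suggests that the authors think an association plausible.

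Stronger readings that a reader might infer, and that the documents do not support:

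- **That the word match makes the unpaired t-test wrong.** Section 6.2 describes equal sex composition, not matched pairs.
- **That the precision loss and the bias add up.** The first belongs to 15/15 and the second to a missed balance.
- **That adjustment costs nothing and always narrows the error.** Step 4 shows otherwise under imbalance. Nor do the two analyses then estimate the same quantity: one compares groups as recruited, the other at equal sex mix.
- **That the age contrast is seriously biased.** At 20 versus 10 women the bias would be 0.07, 0.10 and 0.17 SD for the same three values of *s*, but nothing in the protocol points to so large an imbalance.
- **That season does confound the comparison.** The protocol states no balancing over the calendar, but nothing shows that the age groups will be recruited at different times.

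**Conclusion.** The point holds as a cheap, minor improvement. Sex is balanced by intention and then ignored in all three primary analyses. Under assumed sex differences of 0.2 to 0.5 SD, this costs at most 2.6 points of power if the balance is reached. If the groups end at 18 versus 12 women, it leaves a bias of 0.04 to 0.10 SD. Both figures rest on the assumed sex effect, and the second also on the illustrative imbalance; with no sex effect neither arises. The primary tests as written remain valid at the planned 15/15 split. The case for carrying season in the same models rests on the protocol's own description of seasonal differences as strong and on the November-to-May window. Its size cannot be computed from the document.

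**What to change.** Amend section 8.4, and the general rule in 8.3 to agree with it, before any data are seen; adding sex only after an imbalance shows would be a post-hoc choice.

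1. **AUC and onset/offset:** use a linear model with age group and sex as the primary analysis, on the log scale where needed, as 8.3 already allows. Keep the unpaired t-test as supporting.
2. **24-hour pattern:** add sex as a between-subjects factor in the repeated measures ANOVA, including its interaction with time, so that the group-by-time comparison is adjusted too.
3. **Coding:** section 6.2 balances on sex while 6.3.1 records gender with four options. State how participants who answer diverse or give no answer enter the model.
4. **Season:** include day length at each participant's recording dates as a covariate in the same models. A linear calendar date would fit poorly, because daylight falls and then rises between November and May.

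The cost is a few sentences and, in the linear models, one degree of freedom of 58 for sex and one more for day length. If the split is 18 versus 12 and sex has no effect, the SE is about 2% wider. No new data collection is needed.
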